10.9.8.8.11. Additional Procedures for Monitoring of Potential Myocarditis or Pericarditis

Any study participant who reports acute chest pain, shortness of breath, palpitations, or any other symptom(s) that might be indicative of myocarditis or pericarditis within 4 weeks after study vaccination (Vaccination 1 or 2) must be specifically evaluated by a cardiologist for possible myocarditis or pericarditis. The same applies for any participant in whom a new ECG abnormality (compared to baseline) consistent with probable or possible myocarditis or pericarditis (as listed in Section 8.2.7) or abnormal troponin I level is observed at Visit 2 or 3.

In addition to a clinical evaluation, the following should be performed:

- ECG and
- Measurement of the troponin level

For any participant in whom a new ECG abnormality (compared to baseline) consistent with probable or possible myocarditis or pericarditis (as listed in Section 8.2.7) or abnormal troponin I level is observed at Visit 2 or 3, this should be achieved by repeating the assessments with the central vendor(s).

If myocarditis or pericarditis is suspected based upon the initial evaluation, the following should also be performed:

- Cardiac echocardiogram and/or
- Cardiac magnetic resonance study

Details of the symptoms reported, and results of the investigations performed, will be recorded in the CRF.

10.9.9. Substudy A Statistical Considerations

See Section 9 for general statistical considerations and phase specifics below.

10.9.9.1. Statistical Hypotheses

There are no statistical hypotheses in Substudy A.

10.9.9.1.1. Estimands

The estimands corresponding to the primary, secondary, and exploratory objectives are described in the table in Section 10.9.3.

10.9.9.1.2. Multiplicity Adjustment

There is no multiplicity adjustment for Phase 1 of the study as all analyses are descriptive in nature.

10.9.9.2. Analysis Sets

See Section 9.2 for defined analysis sets.

10.9.9.3. Statistical Analyses

The SAP will be developed and finalized for this phase before any analyses are performed and will describe the analyses and procedures for accounting for missing, unused, and spurious data. This section is a summary of the planned statistical analyses of the primary and secondary endpoints.

10.9.9.3.1. General Considerations

See Section 9 for general considerations of statistical analyses.

Note that, if a clear HAI result is not obtainable for any strain, neutralizing titers will replace HAI titers as the main immunogenicity endpoint for that strain.

[figure not shown]
10.9.9.3.2. Primary Endpoint(s)/Estimand(s) Analysis

[figure not shown]
Endpoint	Statistical Analysis Methods
Safety	• Point estimates and the associated exact 2-sided 95% CIs will be calculated using the Clopper-Pearson method for the proportion of participants reporting each event (local reactions, systemic events, and AEs) for each vaccine group after Vaccinations 1 and 2.
	 Point estimates and the associated exact 2-sided 95% CIs will be calculated using the Clopper-Pearson method for the proportion of participants reporting each event (SAEs) for each vaccine group after the last vaccination.
	• Point estimates and the associated exact 2-sided 95% CIs will be calculated using the Clopper-Pearson method for the proportion of participants reporting each event (abnormal hematology and chemistry laboratory) for each study vaccine at 2 days and 1 week after Vaccination 1.
	• Point estimates and the associated exact 2-sided 95% CIs will be calculated using the Clopper-Pearson method for the proportion of participants reporting grading shifts in hematology and chemistry laboratory assessment between baseline and 2 days, and 1 week, after Vaccination 1.
	• Point estimates and the associated exact 2-sided 95% CIs will be calculated using the Clopper-Pearson method for the proportion of participants with new ECG abnormalities at 2 days and 1 week after Vaccination 1.

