8.3.1. Time Period and Frequency for Collecting AE and SAE Information

The time period for actively eliciting and collecting AEs and SAEs ("active collection period") for each participant begins from the time the participant provides informed consent, which is obtained before the participant's participation in the study (ie, before undergoing any study-related procedure and/or receiving study intervention), through and including:

- Visit 4 (4-week follow-up visit), and from Visit 5 to Visit 5B (4-week post-Vaccination 2 follow-up visit) for Substudy A. Additionally, for Substudy A, any AEs occurring up to 48 hours after the blood draws at Visits 4 and 5B must be recorded on the CRF.
- Visit 206 (4-week follow-up visit) for Substudy B. Additionally, for Substudy B, any AEs occurring up to 48 hours after the blood draws at Visits 206 and 207 must be recorded on the CRF.

SAEs will be collected from the time the participant provides informed consent to approximately 6 months after the participant's last study vaccination (Visit 6 for Substudy A and Visit 208 for Substudy B).

Follow-up by the investigator continues throughout and after the active collection period and until the AE or SAE or its sequelae resolve or stabilize at a level acceptable to the investigator.

For participants who are screen failures, the active collection period ends when screen failure status is determined.

If the participant withdraws from the study and also withdraws consent for the collection of future information, the active collection period ends when consent is withdrawn.

If a participant permanently discontinues or temporarily discontinues study intervention because of an AE or SAE, the AE or SAE must be recorded on the CRF and the SAE reported using the Vaccine SAE Reporting Form.

Investigators are not obligated to actively seek information on AEs or SAEs after the participant has concluded study participation. However, if the investigator learns of any SAE, including a death, at any time after a participant has completed the study, and he/she considers the event to be reasonably related to the study intervention, the investigator must promptly report the SAE to Pfizer using the Vaccine SAE Reporting Form.

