10.9.3. Objectives, Endpoints, and Estimands (Substudy A)

[figure not shown]
For the purposes of the study estimands:

• Seroconversion is defined as an HAI titer <1:10 prior to vaccination and ≥1:40 at the time point of interest, or an HAI titer of ≥1:10 prior to vaccination with a 4-fold rise at the time point of interest.

Objectives	Estimands	Endpoints
Primary Safety:	Primary Safety:	Primary Safety:
To describe the safety and tolerability of mIRV, bIRV, and qIRV in adults 65 to 85 years of age	In participants receiving at least 1 dose of study intervention, the percentage of participants reporting: • Local reactions for up to 7 days following Vaccinations 1 and 2 • Systemic events for up to 7 days following Vaccinations 1 and 2 • AEs 4 weeks after Vaccinations 1 and 2 • SAEs from the first vaccination to 6 months after the last vaccination	 Local reactions (pain at the injection site, redness, and swelling) Systemic events (fever, fatigue, headache, chills, vomiting, diarrhea, new or worsened muscle pain, and new or worsened joint pain) AES SAES
	The percentage of participants with: Abnormal hematology and chemistry laboratory values 2 days and 1 week after Vaccination 1 Grading shifts in hematology and chemistry laboratory assessments between baseline and 2 days and 1 week after Vaccination 1	Hematology and chemistry laboratory parameters detailed in Section 10.2
	The percentage of participants with: New ECG abnormalities 2 days and 1 week after Vaccination 1	ECG abnormalities consistent with probable or possible myocarditis or pericarditis as defined in Section 8.2.7
Secondary:	Secondary:	Secondary:
To describe the immune responses elicited by mIRV, bIRV, and qIRV in adults 65 to 85 years of age	In participants complying with the key protocol criteria (evaluable participants) at 1, 4, and 8 weeks after receipt of Vaccination 1: • HAI GMTs at 1, 4, and 8 weeks after receipt of Vaccination 1 • HAI GMFR from before Vaccination 1 to 1, 4, and 8 weeks after receipt of Vaccination 1 • The proportion of participants achieving HAI seroconversion for each strain at 1, 4, and 8 weeks after receipt of Vaccination 1	HAI titers for each strain targeted by the study vaccine

PFIZER CONFIDENTIAL

Objectives	Estimands	Endpoints
	• The proportion of participants with HAI titers ≥1:40 for each strain before Vaccination 1 and at 1, 4, and 8 weeks after receipt of Vaccination 1	

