- bIRV: CCl in dose level combinations shown in Section 1.2
- qIRV: CCI

Dependent upon safety and/or immunogenicity data generated during this phase, it is possible that additional bIRV groups may be initiated to study further dose level and strain combinations.

Participants from the initial enrollment period will be unblinded at Visit 5 (8 weeks after Vaccination 1) and licensed QIV will be administered at Visit 5 to participants not having previously received licensed QIV. Additionally, at Visit 5A, participants who previously received QIV at Visit 1 will receive either:

- mIRV at a dose level of cencoding A strain (up to 30 participants who previously received licensed QIV at Visit 1), or
- mIRV at a dose level of CC encoding B strain (up to 30 participants who previously received licensed QIV at Visit 1).

Vaccinations administered at either Visit 5 or Visit 5A will be considered Vaccination 2 for these participants.

Following implementation of protocol amendment 2, all participants will be asked to complete a reactogenicity e-diary for 7 days following Vaccination 2. Blood samples of approximately 50 mL will be collected for immunogenicity assessments prior to Vaccination 2 and 4 weeks afterwards.

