10.10.9.3.2. Primary Endpoint(s)/Estimand(s) Analysis

Endpoint	Statistical Analysis Methods
Safety (adults 65 to 85 years of age)	• Point estimates and the associated exact 2-sided 95% CIs will be calculated using the Clopper-Pearson method for the proportion of participants reporting each event (local reactions and systemic events) for each vaccine group for up to 7 days following each vaccination.
	• Point estimates and the associated exact 2-sided 95% CIs will be calculated using the Clopper-Pearson method for the proportion of participants reporting each AE from the first vaccination to 4 weeks after the last vaccination, by vaccination group.
	• Point estimates and the associated exact 2-sided 95% CIs will be calculated using the Clopper-Pearson method for the proportion of participants reporting each SAE from the first vaccination to 6 months after the last vaccination, by vaccination group.
	• Point estimates and the associated exact 2-sided 95% CIs will be calculated using the Clopper-Pearson method for the proportion of participants reporting abnormal troponin I levels for each study vaccine at 2 days after the last vaccination.
	• Point estimates and the associated exact 2-sided 95% CIs will be calculated using the Clopper-Pearson method for the proportion of participants with new ECG abnormalities at 2 days after the last vaccination.

[figure not shown]
Endpoint	Statistical Analysis Methods		
Safety (adults 18 to 64 years of age)	• Point estimates and the associated exact 2-sided 95% CIs will be calculated using the Clopper-Pearson method for the proportion of participants reporting each event (local reactions and systemic events) for up to 7 days after vaccination.		
	• Point estimates and the associated exact 2-sided 95% CIs will be calculated using the Clopper-Pearson method for the proportion of participants reporting each AE from the first vaccination to 4 weeks after vaccination.		
	• Point estimates and the associated exact 2-sided 95% CIs will be calculated using the Clopper-Pearson method for the proportion of participants reporting each SAE from the first vaccination to 6 months after vaccination.		
	• Point estimates and the associated exact 2-sided 95% CIs will be calculated using the Clopper-Pearson method for the proportion of participants reporting abnormal troponin I levels at 2 days after vaccination.		

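### Substudy A's primary SAE analysis row starts the count at the last vaccination, contradicting its own estimand and omitting events before the second product for participants who cross over

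*Protocol*

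**What the plan says.** The Substudy A primary safety estimand (Protocol Section 10.9.3, repeated in the Section 1.1 synopsis) is the percentage of participants with "SAEs from the first vaccination to 6 months after the last vaccination". The statistical section defers to that table: "The estimands corresponding to the primary, secondary, and exploratory objectives are described in the table in Section 10.9.3" (Section 10.9.9.1.1). Collection matches it: "SAEs will be collected from the time the participant provides informed consent to approximately 6 months after" the last study vaccination (Section 8.3.1).

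The analysis row in Section 10.9.9.3.2 has a different window. It gives the "proportion of participants reporting each event (SAEs) for each vaccine group after the last vaccination". The row above it, for local reactions, systemic events and AEs, reports after each of the two vaccinations. The corresponding Substudy B row (Section 10.10.9.3.2) gives the "proportion of participants reporting each SAE from the first vaccination to 6 months after the last vaccination".

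Under Section 10.9.4.1, "licensed QIV will be administered at Visit 5 to participants not having previously received licensed QIV", and "at Visit 5A, participants who previously received QIV at Visit 1 will receive either" mIRV A or mIRV B. It adds: "Vaccinations administered at either Visit 5 or Visit 5A will be considered Vaccination 2 for these participants". Section 10.9.8.8.6 lets a participant refuse Vaccination 2 and go straight to Visit 6.

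**The concern.** If each participant had a single vaccination, the two windows would be the same and the wording harmless. In Substudy A the last vaccination is, for anyone who accepts it, a second and different product given about 8 weeks after the first. A programmer who follows the row would start the SAE count at that dose and leave out everything between the randomized product and the second one.

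This is a primary endpoint, and the objective is to describe the safety of mIRV, bIRV and qIRV. The omitted time is the only part of follow-up in which a modRNA recipient has received the modRNA vaccine and nothing else from the study.

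**Working it through.** **Inputs, all from the Protocol**
- Groups: mIRV A at 4 dose levels, mIRV B at 4, bIRV in 4 combinations, qIRV at 1, and 4 QIV comparator groups, with 15 per group (Sections 1.2.1, 2.1, 9.5 and Table 5).
- Day of Vaccination 2, *v*: 52 to 60 days after Visit 1 for modRNA groups (Visit 5, Section 10.9.8.8.6); 52 to 97 days for QIV groups (Visit 5A, Section 10.9.8.8.7).
- Follow-up after the last vaccination, *f*: 175 to 189 days (Visit 6, Section 10.9.8.8.9).
- AE estimand: 4 weeks after each vaccination (Section 10.9.3).

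**Reproducing the plan's figures**
- modRNA groups: 4 + 4 + 4 + 1 = 13, and 13 × 15 = 195. QIV groups: 4 × 15 = 60. Total: 195 + 60 = 255, as in Section 9.5.
- Table 4, N = 195, using 1 − (1 − p)^195: 0.465, 0.624, 0.859 and 0.981 at p = 0.32%, 0.5%, 1% and 2%. Table 4 prints 0.46, 0.62, 0.86 and 0.98.

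**Share of the estimand window omitted by the literal row, *v*/(*v* + *f*)**
- modRNA groups: lowest 52/(52 + 189) = 21.6%; highest 60/(60 + 175) = 25.5%.
- QIV groups: lowest 52/(52 + 189) = 21.6%; highest 97/(97 + 175) = 35.7%.

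**Time in neither the SAE row nor the AE analysis, if AEs stop at 4 weeks (28 days)**
- modRNA groups: 52 − 28 = 24 to 60 − 28 = 32 days.
- QIV groups: 52 − 28 = 24 to 97 − 28 = 69 days.

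**Illustration of the effect on detection.** The documents give no SAE rate. I assume a risk *r* over the full window, a constant hazard, and crossover by all 195 modRNA recipients. The chance of at least one SAE in the table is 1 − (1 − r)^(195 × share kept), with the share kept between 1 − 0.255 and 1 − 0.216.

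| Assumed r | Full window | Literal row |
|---|---|---|
| 0.5% | 0.62 | 0.52-0.54 |
| 1% | 0.86 | 0.77-0.79 |
| 2% | 0.98 | about 0.95 |

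**What the full window alone leaves mixed.** In QIV recipients who cross over, 175/(97 + 175) = 64.3% to 189/(52 + 189) = 78.4% of the estimand window falls after mIRV. In modRNA recipients who cross over, 175/(60 + 175) = 74.5% to 189/(52 + 189) = 78.4% falls after QIV.

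**The case against.** The best reply is that the row abbreviates the estimand. Section 10.9.9.3 describes itself as a summary and promises an SAP for the phase, Section 10.9.9.1.1 points to the correct estimand table, and SAEs are recorded from consent. That much stands: the defect is a contradiction between two places in the protocol, and events leave the table only if the row is programmed as written. But the supplied SAP is for Substudy B (SAP Section 2), so nothing seen here settles which window will be used. Section 9 also says that major changes to primary endpoint analyses will be reflected in a protocol amendment, so the protocol is the place to correct it.

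Four stronger inferences are tempting, and the documents do not support them.
- *All early SAEs vanish from the primary tables.* SAEs are also recorded as AEs, so those within 4 weeks of Vaccination 1 stay in the AE proportions, without the serious label. The later gap depends on taking the 4-week limit from Section 10.9.3; the AE row in Section 10.9.9.3.2 states no such limit.
- *SAEs after mIRV will be shown as control events, and SAEs after QIV as modRNA events.* Section 9.3.1 groups participants by what they actually received and does not say how a two-product sequence is labelled. Later events also follow both products.
- *The period before Vaccination 2 will never be reported separately.* The Substudy A SAP was not available, so this cannot be established.
- *A planned randomized SAE comparison is lost.* Substudy A has no hypotheses, and the row plans no between-group SAE comparison.

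**Conclusion.** The row is wrong as written: it disagrees with the primary estimand and with its Substudy B counterpart. For participants who take Vaccination 2, it omits 22-26% of the estimand window in the modRNA groups and 22-36% in the QIV groups. These figures assume the literal reading and doses given within the visit windows; Section 10.9.8.8.6 allows QIV to be given when it becomes available, and a later dose would enlarge the omitted share. Uptake of Vaccination 2 is not stated. For those who decline, the last vaccination is Vaccination 1 and nothing is omitted.

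This is an inexpensive correction to a primary-endpoint rule. It does not show that safety data are missing or that the substudy is compromised. Separating SAEs at Vaccination 2 is an improvement in interpretability; its absence is not an error against the stated estimand.

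**What to change.** In Protocol Section 10.9.9.3.2, give the SAE row the window in Section 10.9.3, "SAEs from the first vaccination to 6 months after the last vaccination", and use the same window in the Substudy A SAP. The cost is one phrase; no new data are needed.

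As an addition, show SAEs descriptively in two periods: (a) Vaccination 1 until just before Vaccination 2, by Vaccination 1 product; (b) Vaccination 2 onward, by sequence (modRNA then QIV, QIV then mIRV A, QIV then mIRV B). Participants who decline Vaccination 2 contribute all their follow-up to (a). This follows the AE row, which already reports after each vaccination. It costs one extra table from dates and events already collected; with 15 per group the cells will be small.

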10.9.9.3.3. Secondary Endpoint(s)/Estimand(s) Analysis

Endpoint	Statistical Analysis Methods
Secondary immunogenicity	• HAI GMTs and associated 2-sided 95% CIs will be provided for each strain, by vaccine group, at 1, 4, and 8 weeks after receipt of Vaccination 1.
	• HAI GMFRs from before Vaccination 1 to 1, 4, and 8 weeks after receipt of Vaccination 1, and associated 2-sided 95% CIs, will be provided for each strain, by vaccine group.
	• The proportion of participants achieving HAI seroconversion at 1, 4, and 8 weeks after receipt of Vaccination 1, and the proportion of participants with HAI titers ≥1:40 before Vaccination 1 and at 1, 4, and 8 weeks after receipt of Vaccination 1, and associated 2-sided Clopper-Pearson 95% CIs will be provided for each strain.
	• The proportion of participants achieving HAI seroconversion for all strains (targeted by the study vaccine) at 1, 4, and 8 weeks after receipt of Vaccination 1, and the proportion of participants with HAI titers ≥1:40 for all strains (targeted by the study vaccine) before Vaccination 1 and at 1, 4, and 8 weeks after receipt of Vaccination 1, and associated 2-sided Clopper-Pearson 95% CIs will be provided for participants who received qIRV or licensed QIV at Visit 1.
	• GMRs of HAI titers for each strain in qIRV recipients compared to QIV comparator recipients 4 weeks after Vaccination 1 and associated 2-sided 95% CIs will be provided.
	• The difference in percentage of participants achieving seroconversion for each strain at 4 weeks after Vaccination 1 in qIRV recipients compared to QIV comparator recipients, and associated 2-sided 95% CIs, will be provided. The 2-sided 95% CIs for the difference in percentages of participants achieving seroconversion between vaccine groups will be calculated using the Miettinen and Nurminen method.

10.9.9.3.4. Tertiary/Exploratory Endpoint(s)

10.9.9.3.5. Other Analyses

The data collected for study participants who report any symptom(s) that might be indicative of myocarditis or pericarditis (ECG, troponin level, cardiac echocardiogram, and/or cardiac magnetic resonance study) within 4 weeks after a study vaccination (Vaccination 1 or 2) will be summarized and listed by vaccine group.

10.9.9.4. Interim Analyses

No formal interim analysis will be conducted for this study phase. As the study is open-label to the sponsor, the sponsor will conduct unblinded reviews of the data during the course of the study for the purpose of safety assessment, dose selection, and/or supporting clinical development.

10.9.9.5. Sample Size Determination

See Section 9.5.

10.10. Appendix 10: Substudy B (Phase 1/2)

10.10.1. SoA – Substudy B (Phase 1/2)

Visit Number	Screening	201	202	203	204	205	206	207	208
Visit Description	Screening	Vaccination	1-Week	Vaccination	Day 3	1-Week	4-Week	8-Week	6-Month
Visit Description		1	Post-	2 ^b	Follow-	Follow-	Follow-	Follow-	Telephone
			Vaccination 1		up Visit	up Visit	up Visit	up Visit	Contact
			Visit ^a			1			
Visit Window (Days)	0 to 28 Days	Day 1	6 to 8	19 to 23	2 to 4	6 to 8	26 to 30	52 to 60	175 to 189
	Before		Days	Days After	Days	Days	Days	Days	Days
	Visit 201			Visit 201					
					the nu	mber of a	days indic		cted within tive to the ation
Obtain informed consent	X								
Assign participant number	X								
Obtain demography and medical history data	X								
Obtain details of medications currently taken	X								
Perform physical examination ^c	X	X							
Perform clinical assessment		X							
Measure vital signs (including body	X	X			X				
temperature)									
Measure body temperature				X					
Perform 12-lead triplicate ECG	X	X			X				
Collect blood sample for troponin I laboratory	~2.5 mL	~2.5 mL			~2.5 mL				
testing									
Collect prior COVID-19 vaccine information	X								
Collect details of any licensed influenza	X								
vaccine received in the prior 12 months									
Collect nonstudy vaccine information	X	X	X	X	X	X	X	X	X
Confirm eligibility	X	X		X					
Collect prohibited medication use			X	X	X	X	X	X	
Review troponin I and ECG results		X	X	X		X			
Perform urine pregnancy test on WOCBP	X	X							
Confirm use of contraceptives (if appropriate)	X	X	X	X	X	X	X		

PFIZER CONFIDENTIAL

Visit Number	Screening	201	202	203	204	205	206	207	208
Visit Description	Screening	Vaccination 1	1-Week Post– Vaccination 1 Visit ^a	Vaccination 2 ^b		1-Week Follow- up Visit		Follow-	6-Month Telephone Contact
Visit Window (Days)	0 to 28 Days Before Visit 201	Day 1	6 to 8 Days	19 to 23 Days After Visit 201	2 to 4 Days	6 to 8 Days	26 to 30 Days	52 to 60 Days	175 to 189 Days
					the nu	mber of d	days indic		cted within tive to the ation
Obtain randomization number and study intervention allocation		X							
Collect blood sample for immunogenicity assessment		~50 mL		~50 mL		~50 mL	~50 mL	~50 mL	
Collect blood sample for cell-mediated immunogenicity assessment ^d		~50 mL	~ 50 mL			~50 mL	~50 mL		
Administer study intervention		X		X					
Assess acute reactions for at least 30 minutes after study intervention administration		X		X					
Explain to the participant e-diary completion requirements and assist the participant with downloading the app or issue provisioned device if required		X							
Provide thermometer and measuring device		X							
Review reactogenicity e-diary data (daily review is optimal during the active diary period)		-		•			•		
Review ongoing reactogenicity e-diary symptoms and obtain stop dates			X	X		X	X		

Visit Number	Screening	201	202	203	204	205	206	207	208
Visit Description	Screening	Vaccination	1-Week	Vaccination	Day 3	1-Week	4-Week	8-Week	6-Month
Visit Description		1	Post-	2 ^b	Follow-	Follow-	Follow-	Follow-	Telephone
			Vaccination 1		up Visit	up Visit	up Visit	up Visit	Contact
			Visita						
Visit Window (Days)	0 to 28 Days	Day 1	6 to 8	19 to 23	2 to 4	6 to 8	26 to 30	52 to 60	175 to 189
	Before		Days	Days After	Days	Days	Days	Days	Days
	Visit 201			Visit 201					
					the nu	mber of d	days indic		cted within tive to the ation
Collect AEs and SAEs as appropriate	X	X	X	X	X	X	Xe	Xe	X
Collect e-diary or assist the participant with deleting application						Xf	X		

Abbreviations: COVID-19 = coronavirus disease 2019; ECG = electrocardiography.

- a. Visit 202 is to be conducted during initial enrollment for participants assigned to a 2-visit vaccination schedule only.
- b. Vaccination 2 (Visit 203) is only conducted for participants randomized to receive a 2-visit vaccination schedule.
- c. Physical examination at Visit 201 will be conducted if clinically indicated.
- d. Additional 50 mL for cell-mediated immunogenicity assessments as detailed in Section 10.10.4.
- e. Any AEs occurring up to 48 hours after the blood draw must be recorded (see Section 8.3).
- f. If Visit 205 is conducted after Day 7.

